#### 4.2 Number of Study Participants

The study population will comprise approximately 1000 healthy US adults who meet the eligibility criteria listed in Section 4.4.

Approximately 800 eligible subjects aged 50 to 64 years (with a minimum of 200 subjects aged 60 to 64 years) and a minimum of 200 subjects aged 65 years and older will be enrolled.

#### 4.3 Estimated Study Duration

The Screening period is 30 days, the Treatment and Observation period is from Day 1 to Month 1 (30 days after vaccination), and the Follow-Up period is through Month 6 (180 days after study vaccination). The maximum possible study duration for an individual is 7 months (210 days).

## **4.4 Study Population**

### **4.4.1 Inclusion Criteria**

Subjects must meet all of the following criteria to be enrolled:

- 1) Male or female aged 50 to 64 years (inclusive) for Stage 1, or 50 years and older (inclusive) for Stage 2 at the time of randomization into the study.
- 2) Able and willing to complete the informed consent process.
- 3) Available for clinical follow-up through the last study visit at 6 months after the study vaccination.
- 4) In good general health as determined by medical history, vital signs, physical examination, and clinical judgment of the Investigator.
- 5) Willing to have blood samples collected, stored indefinitely, and used for research purposes.
- 6) Able to provide proof of identity to the satisfaction of the study staff completing the enrollment process.
- 7) Women of childbearing potential, defined as premenopausal females capable of becoming pregnant, must have a negative urine pregnancy test immediately prior to randomization and agree to use acceptable contraception, defined as: condoms, male or female, with or without a spermicide; diaphragm or cervical cap with spermicide; intrauterine device; contraceptive pills or patch, Norplant, Depo-Provera; or a female with a male partner that has previously undergone a vasectomy. Subjects must agree to consistently practice contraception if sexually active at least 7 days prior to enrollment and throughout the duration of the study.
- 8) Able to access and use a smartphone, tablet, computer, or other device connected to Wi-Fi or cellular network for completion of an electronic diary.

### **4.4.2 Exclusion Criteria**

Subjects who meet any of the following criteria cannot be enrolled:

- 1) Previous pneumococcal disease (either confirmed or self-reported).
- 2) Previous receipt of a licensed or investigational pneumococcal vaccine.
- 3) Receipt of any investigational study product within 30 days prior to enrollment into the study, currently participating in another interventional investigational study, or having plans to receive another investigational product(s) while on study.

- 4) Planned or actual administration of any licensed vaccine during the period starting 30 days before enrollment into the study through Month 1.
- 5) Physical examination indicating any clinically significant medical condition.
- 6) Body Temperature  $>38.0^{\circ}\text{C}$  ( $>100.4^{\circ}\text{F}$ ) or acute illness within 3 days prior to study vaccination (subject may be rescheduled).
- 7) Previous or existing diagnosis of HIV, Hepatitis B, or Hepatitis C.
- 8) History of severe allergic reaction with generalized urticaria, angioedema, or anaphylaxis.
- 9) Female who is pregnant, breastfeeding, or planning to become pregnant during study participation.
- 10) Bleeding disorder diagnosed by a doctor (e.g., factor deficiency, coagulopathy, or platelet disorder requiring special precautions) resulting in clinically significant bruising or bleeding difficulties with IM injections or blood draws.
- 11) Any other chronic or clinically significant medical condition that, in the opinion of the Investigator, would jeopardize the safety or rights of the subject or confound evaluation of the study vaccine, including but not limited to diabetes mellitus type I, untreated hypertension, chronic hepatitis or clinically significant forms of drug or alcohol abuse, asthma, autoimmune disease, psychiatric disorders, heart disease, pulmonary disease, neurologic disease, cancer, or any known or suspected impairment of immune function.
- 12) Any medical, psychiatric, or social condition that in the judgment of the Investigator is a contraindication to protocol participation or impairs a subject's ability to give informed consent.
- 13) Received blood or blood product (including Immune Globulin IV) within 90 days prior to enrollment into the study.
- 14) Received systemic corticosteroids (except for inhaled, topical, intra-articular) for  $\geq 14$  consecutive days and has not completed treatment  $\leq 30$  days prior to enrollment into the study.
- 15) Receiving immunosuppressive therapy, including chemotherapeutic agents used to treat cancer or other conditions, immunostimulants, and treatments associated with organ or bone marrow transplantation, or autoimmune disease.
- 16) History of malignancy  $\leq 5$  years before enrollment, except for adequately treated basal cell or squamous cell skin cancer or in situ cervical cancer.

## 5. Study Vaccine

## 5.1 Investigational Vaccine (VAX-31)

VAX-31 is the Sponsor's research name for a 31-valent pneumococcal conjugate vaccine.

VAX-31 comprises capsular polysaccharide antigens of *S. pneumoniae* serotypes 1, 2, 3, 4, 5, 6A, 6B, 7C, 7F, 8, 9N, 9V, 10A, 11A, 12F, 14, 15A, 15B, 16F, 17F, 18C, 19A, 19F, 20B, 22F, 23A, 23B, 23F, 31, 33F, and 35B, with each of the 31 polysaccharides (1 from each serotype) individually conjugated in a site-specific manner to a proprietary non-toxic diphtheria carrier protein referred to as eCRM.

■ Each vial is filled to deliver a single 0.5 mL dose of VAX-31 vaccine for IM administration, with no preservative. VAX-31 is manufactured by Laboratoire Baccinex (Switzerland) and will be supplied at 3 strengths in single-use 2 mL glass vials. The vial is sealed with a 13 mm bromo butyl rubber stopper with FluroTec® coating on the side in contact with VAX-31 DP. The stopper is capped with a 13 mm crimped aluminum seal with a flip-off white cap for the Low dose level, a blue cap for the Mid dose level, and a natural colored cap for the High dose level.

The 3 different dose levels of VAX-31 will be identified as:

- Low, 1.1 mcg of Polysaccharide (PS)/dose per serotype
- Mid, 2.2 mcg of PS/dose per serotype
- High, 3.3 mcg of PS/dose per serotype.

Conjugate Drug Substance serotypes 1, 5, and 22F are present at 1.65 mcg for Low, 3.3 mcg for Mid, and 4.4 mcg for High dose levels.

The amount of eCRM also varies by dose level. The Low dose level contains ~30 mcg of eCRM, the Mid dose level contains ~60 mcg of eCRM, and the High dose level contains ~90 mcg of eCRM.

VAX-31 must be stored in a temperature-controlled refrigerator at 2°C to 8°C with controlled, limited access to authorized personnel only. The temperature should be monitored by checking and recording current and maximum/minimum temperature readings inside the vaccine storage unit at least once each working day and/or before dosing subjects that day.

### **5.1.1 Active Comparator**

Prevnar 20 (PCV20), 20-valent pneumococcal conjugate vaccine, is a sterile suspension of saccharides of the capsular antigens of *S. pneumoniae* serotypes 1, 3, 4, 5, 6A, 6B, 7F, 8, 9V, 10A, 11A, 12F, 14, 15B, 18C, 19A, 19F, 22F, 23F, and 33F individually linked to nontoxic diphtheria CRM197 protein. PCV20 is manufactured by Wyeth Pharmaceuticals, LLC (subsidiary of Pfizer Inc.) and is commercially available in the US. Each 0.5 mL dose of the vaccine is formulated to contain approximately 2.2 mcg of each *S. pneumoniae* serotypes 1, 3, 4, 5, 6A, 7F, 8, 9V, 10A, 11A, 12F, 14, 15B, 18C, 19A, 19F, 22F, 23F, and 33F; 4.4 mcg of the polysaccharide from serotype 6B; 51 mcg CRM197 carrier protein; and 100 mcg polysorbate 80, 295 mcg succinate buffer, 4.4 mg sodium chloride, and 125 mcg aluminum as aluminum phosphate adjuvant. PCV20 prefilled syringes (PFS) are to be stored at 2°C to 8°C (36°F to 46°F), as required by the manufacturer.

Refer to the PCV20 Package Insert for clinical dosage and administration, storage and handling, contraindications, warnings and precautions, and summary of clinical study results.

### **5.1.2 Ancillary Supplies**

The following supplies are provided by the Sponsor for preparation and administration of study vaccine:

- 1 mL BD Luer-Lok™ Syringe sterile, single use polycarbonate
- 1-1/2 inch 25 Gauge Safety Hypodermic Needle Eclipse BD™ single use, sterile

## **5.2 Dose Preparation of Study Vaccines**

A central supply depot(s) will provide study vaccines and ancillary supplies.

Unblinded site personnel will manage all aspects of the vaccine inventory; prepare the vaccine for administration; administer the vaccine and active comparator to study subjects; and store and monitor the vaccine in a secure area and maintain all accountability documentation. All study site personnel who complete subject assessments will be blinded to the vaccines being administered to study subjects. Unblinded site personnel will be trained in all aspects of vaccine management, preparation, and administration, and will be provided a Pharmacy Manual regarding such procedures.

### **5.2.1 VAX-31**

VAX-31 should be inspected visually for particulate matter and discoloration prior to administration. The product should not be used, and the Sponsor should be notified if particulate matter or discoloration is found. VAX-31 is a suspension containing ALPO and should be

shaken vigorously (for at least 15 seconds) immediately prior to use to obtain a homogenous, white suspension in the vaccine container. The vaccine should not be used if it cannot be resuspended. All VAX-31 doses are to be withdrawn into Sponsor-provided syringes using sterile technique. No dilution or reconstitution is necessary. VAX-31 vials must be stored upright and brought to room temperature ( $\geq 10$  minutes) and administered between 10 to 60 minutes, inclusive, from the time the vaccine is removed from the refrigerator. Detailed instructions on packaging, preparation, administration, and accountability are found in the VAX31-101 Pharmacy Manual.

### **5.2.2 PCV20**

PCV20 prefilled syringes (PFS) should be inspected visually for particulate matter and discoloration prior to administration. The vaccine should not be used and the Sponsor should be notified if particulate matter or discoloration is found. PCV20 is a suspension containing ALPO and should be shaken vigorously immediately prior to use to obtain a homogenous, white suspension in the vaccine container. The vaccine should not be used if it cannot be resuspended. PCV20 will be supplied to the clinical sites as single-use PFS packaged by the manufacturer and should be stored horizontally. PCV20 should be administered by IM injection as soon as possible after being removed from refrigeration. Preparation and administration instructions are found in the PCV20 Prescribing Information (manufacturer's package insert) and should be adhered to.

### **5.2.3 Study Vaccine Administration**

Each vaccine (VAX-31 or PCV20) is to be administered IM as a single dose in the deltoid muscle of the upper arm.

## **5.3 Accountability Procedures for Study Vaccines**

It is the responsibility of the Investigator to supervise accurate monitoring of the receipt, storage, dispensing, and accounting of all study vaccines according to accepted industry practice. Sites must maintain and retain accurate, original site records of study vaccine inventory as well as all shipping documentation, including temperature data, invoices of shipments and records of study vaccine distribution.

Vaccine accountability information will be collected on paper source documents for tracking study vaccines (e.g., date material was received, dispensed to individual subjects, and amount used and unused on site etc.).

Each site must keep all used study vaccine cartons until the unblinded CRA has performed vaccine accountability and arranges return of unused study vaccines to the central repository

vendor. Expired vaccine should be separately quarantined until the unblinded CRA has completed accountability monitoring.

Detailed instructions on packaging, preparation, administration, and accountability are found in the VAX31-101 Pharmacy Manual.

## **6. Study Procedures**

Source documents and source data should meet the elements of data quality and integrity (ALCOA-C: attributable, legible, contemporaneous, original, accurate, and complete).

### **6.1 Informed Consent**

The Investigator must obtain informed consent from study subjects at the Screening visit prior to starting any study-related activities. All prospective subjects must sign and date an Institutional Review Board (IRB)-approved ICF. For further details on informed consent, refer to Section [11.3](#).

### **6.2 Screening**

Screening procedures are listed in the Schedule of Events ([Appendix A](#)).

Each subject who signs an ICF will receive a sequential 3-digit identification number unique to the site (e.g., 001, 002, etc.). Upon entry of a subject into the Screening Form within the electronic data capture (EDC) system, Zelta, each subject will be automatically assigned a unique Subject identifier. This Subject ID will be in the following format:

Study Number – 2-digit site number – 3-digit identification number: **VAX31-101-01-001**

Subject numbers will also be sequential since screen-failed subjects will be entered into the EDC system.

Each site is required to record the reason(s) for screen failure for all subjects who receive a subject identification number within the EDC system. Sites may elect to use a prescreening consent form and maintain a prescreening log for those subjects contacted for the study and will provide that log to the Sponsor or designee on request.

**Rescreening:** A subject who meets exclusion criterion of having a current acute febrile illness at the time of scheduled enrollment may be rescreened after resolution of the acute illness. A subject who has taken any prohibited medication within the exclusionary window may be rescreened after the appropriate duration has passed. If an eligible subject is not able to be randomized and treated within 30 days of the screening period, all screening procedures must be

conducted again, including reconsenting and assigning a new subject ID number. A subject may be rescreened once only. Rescreening is not otherwise permitted.

If a subject is rescreened outside of the initial 30-day screening window, a new subject number will be assigned as they are entered into the EDC for a new Screening visit and the previous subject number will be captured in the source file of the newly assigned subject number.

### **6.3 Medical History**

Medical history information will be collected from subjects at the Screening Visit and confirmed at the Day 1 (Baseline) Visit. Medical history will include but not be limited to demographic information, current and past medical conditions, and prior and concomitant medications taken within 30 days prior to Day 1, including history of vaccinations.

In consideration of the availability of commercial pneumococcal vaccines and ongoing investigational vaccine clinical research, the history of pneumococcal vaccination must be collected and, if the subject's medical records and/or state-mandated vaccine registry are available, the site is required to maintain this documentation as part of the eligibility review.

### **6.4 Physical Examination**

A complete physical examination will be performed on subjects during the Screening visit. The examination should include:

- Height
- Body weight
- Vital signs
- General appearance
- Eyes-ears-nose-throat
- Head-neck
- Lungs-chest
- Heart
- Abdomen
- Musculoskeletal
- Lymph nodes
- Skin
- Extremities
- Neurological

A physical exam may be performed on subjects at additional time points if indicated by AE reporting.

### **6.5 Vital Signs**

Vital signs collected from subjects will include blood pressure, heart rate, respiratory rate, and oral temperature. The first set of Screening vitals are to be collected for inclusion of the subject into the study. Repeat measurements on abnormal vital parameters are allowed 1 additional time

for inclusion into the study. After Day 1, abnormal vital signs can be repeated for confirmation of clinical significance. Vital signs should be taken after at least 5 minutes in supine position.

## 6.6 Laboratory Tests

### 6.6.1 Blood Volume

Blood is collected by venipuncture, in the appropriate blood container tubes according to the schedule of sample collection shown in [Appendix A](#) and Table 1. The maximum volume of blood taken from a subject is 43 mL. Phlebotomy will observe the American Red Cross limit of no more than 450 mL in any 8-week period.

**Table 1** Blood Collections

Study Day	Blood Volume (mL)	Laboratory Tests	Tube Type/Volume	Minimum No. of 1 mL Cryovials
Day 1	21.5 mL	Hematology Clinical Chemistry Immunogenicity	1 EDTA 2 mL 1 SST 2.5 mL 2 SST 8.5 mL	Not applicable Not applicable 12
Month 1	21.5 mL	Hematology Clinical Chemistry Immunogenicity	1 EDTA 2 mL 1 SST 2.5 mL 2 SST 8.5 mL	Not applicable Not applicable 12

**Note:** All cryovials should be frozen and stored at -20°C or colder and shipped on dry ice.

Samples are obtained during the trial according to Appendix A. At each time point, blood is collected in the appropriate blood tube(s).

To minimize the impact of lost or damaged shipments, the frozen serum samples will be sent in separate consignments (on different days to minimize risk of transport delays or loss) to the central laboratory.

Further details regarding specimen collection, processing, and shipping will be provided in the Central Laboratory Manual.

### 6.6.2 Safety Laboratory Assessments

Biological samples will be collected for the following clinical laboratory tests and shipped to the central laboratory for analysis:

- **Hematology:** Hemoglobin, White blood cell count (absolute), Neutrophils (absolute), Eosinophils (absolute), Platelet count, Blood Film Review, Manual Differential (Panel)

- **Clinical Chemistry:** Albumin, Alkaline phosphatase, Alanine aminotransferase (ALT), aspartate aminotransferase (AST), Bilirubin (total and direct), Blood urea nitrogen, Calcium, Carbon dioxide, Chloride, Cholesterol and triglycerides, Creatinine, Glucose (random), Gamma-glutamyl transferase (GGT), Lactate dehydrogenase, Phosphate, Potassium, Sodium, Total serum protein, Uric acid
- **Urinalysis:** Specific gravity, pH, Glucose, Protein (Total), Ketones, Bilirubin, Urobilinogen, Hemoglobin, Leucocyte esterase, Nitrite

Urine pregnancy tests will be conducted at the site using a dipstick before vaccination.

Unscheduled laboratory tests will be performed if indicated by a change in medical condition (including clinically significant abnormal values). The volume to be collected will be appropriate to the tests performed. The toxicity grading scales for clinical laboratory values ([FDA, 2007](#)) must be used when assigning severity to an out-of-range laboratory value; however, not all out of range laboratory values are considered AE and need to be evaluated according to Section [8.1.1](#).

Further details regarding specimen collection, processing, and shipping will be provided in the Central Laboratory Manual.

### 6.6.3 Immune Response Assessments

Immunogenicity samples should be collected for all subjects randomized in the study. Serum antibody responses to pneumococcal polysaccharides induced by vaccination will be measured using 2 standard assays, OPA and multiplexed Meso Scale Discovery (MSD).

The OPA assay has been developed and qualified by NEXELIS, a GCP-compliant central laboratory, to analyze the functional responses to 31 polysaccharide antigens contained in VAX-31. The OPA assay has been consistently used as the method for measuring the functional capacity of pneumococcal antibodies, as antibodies to pneumococcal PS protect the host by opsonizing pneumococci (marking pneumococci for destruction) for phagocytosis ([Burton, 2012](#)).

The MSD assay has been developed and qualified by NEXELIS to measure IgG responses against the 31 polysaccharide antigens contained in VAX-31. The MSD multiplex electrochemiluminescent assay is an immunoassay platform that allows simultaneous measurement of responses against multiple antigens and has been used to evaluate responses to various PCV ([Feyssaguet, 2019](#); [Goldblatt, 2011](#); [Marchese, 2009](#); [Nolan, 2020](#)).

The immune responses (as assessed by OPA and MSD assays) against the 20 polysaccharide antigens common to PCV20 and VAX-31 (1, 3, 4, 5, 6A, 6B, 7F, 8, 9V, 10A, 11A, 12F, 14, 15B,

18C, 19A, 19F, 22F, 23F and 33F) will be compared in the various treatment groups (VAX-31 at 3 different dose levels, and the comparator vaccine), and the 11 additional polysaccharide antigens contained in VAX-31 (2, 7C, 9N, 15A, 16F, 17F, 20B, 23A, 23B, 31 and 35B) will be evaluated separately.

## 6.7 Pregnancy Testing and Contraception

Female subjects of childbearing potential, defined as premenopausal females capable of becoming pregnant, will undergo a urine pregnancy test at Screening and immediately prior to vaccination. The subject must have a negative pregnancy test prior to study vaccine administration. The Investigator must report any pregnancies as described in Section 8.7.1. Female subjects of childbearing potential must also use an acceptable method of contraception from prior to Day 1 through Month 6 (throughout the study). The Investigator must confirm that contraception methods were initiated prior to Day 1 (e.g., hormonal contraception) to be considered fully effective.

For reporting a pregnancy, refer to Section 8.7.1.

## 6.8 Randomization

Subject eligibility will be confirmed and documented by the Investigator immediately prior to randomization of each subject.

Blinded study staff will indicate on a Randomization electronic Case Report Form (eCRF) within the EDC system that they want to generate a randomization number for the subject. When they indicate yes, a randomization number will be generated from EDC. The randomization number is separate from, and does not replace, the subject identification number which is assigned at Screening. The unblinded designee will receive information from the Zelta EDC with treatment assigned for VAX-31 (1.1/1.65 mcg, 2.2/3.3 mcg, or 3.3/4.4 mcg dose) or treatment assigned PCV20 PFS. The unblinded designee may then prepare the treatment assigned for administration.

Randomization will be 1:1:1:1 for the 4 treatment groups across the sample size (1000 subjects). For Stage 1, there were no stratification factors. For Stage 2, randomization will be stratified by each of the 25 clinical sites. See Section 10.3 for further details on the sample sizes within each age group.

A subject will be considered enrolled once a randomization number has been assigned within the EDC system. The study will be conducted as an observer-blind study. No one except specific predesignated unblinded staff (at sites and CRO) will know subjects' individual treatment assignments until all subjects have completed their participation in the study and the database has been cleaned and locked.

The following safeguards will be employed to reduce the risk of inadvertent unblinding:

- Each clinical site is required to have a blinding plan that outlines its process on blinding the subject in situations such as administration of IM injection with different syringe types, transport of study vaccine to the clinic room for administration, providing initial training and reminders to the subjects on how to maintain the study blind.
- No Sponsor personnel other than the designated unblinded monitor(s), Sponsor unblinded Oversight Representative, third-party unblinded biostatistics and programming staff, and the Sponsor Medical Director, if necessary, will have access to the randomization treatment assignments. If Sponsor personnel are unblinded, they will not provide input on data for the specific subject they were unblinded to.
- Should any subject or blinded staff member become inadvertently unblinded, the Investigator will promptly (within 24 hours of the Investigator's awareness of the error) disclose the event to the Sponsor clinical study manager and medical monitor in a blinded fashion (disclosing only subject number, not treatment) so that corrective action can be initiated. The unblinding sequence of events will be documented as a protocol deviation and retained as source documents. See Section [6.15](#) for details on Emergency Unblinding.

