## Study Design

This Phase 1/2 parallel-group, randomized, 2 stage observer-blind study is to be conducted in 3 populations of healthy adults, aged 50 to 59, 60 to 64, and 65 years and older. Subjects will be randomly assigned in a 1:1:1:1 ratio to receive either VAX-31 at 1 of 3 dose levels or a single dose of PCV20, the active comparator.

In Stage 1 of the study, 64 subjects (16 for each VAX-31 dose group and 16 for the comparator group) 50 to 64 years of age will be enrolled initially. In Stage 2, approximately 736 additional adults aged 50 to 64 years as well as a minimum of 200 adults aged 65 years and older will be concurrently enrolled. Subjects will have screening procedures (physical examination, vital signs, urine pregnancy test for females of childbearing potential), and if eligible, will be enrolled into the study. All subjects will have a urine sample collected as well as blood samples drawn for immunogenicity analysis (OPA and IgG) and safety laboratory analysis at Day 1 (predose) and Month 1 (30 days after vaccination). Subjects will receive VAX-31 or PCV20 on Day 1. Solicited AE will be collected for 7 days after vaccination and unsolicited safety information for 30 days after vaccination, with SAE, NOCI, and MAAE collected up to 6 months after vaccination.

A defined safety review of data (solicited and unsolicited AE and SAE) through 7 days after vaccination of the 64 subjects in Stage 1 will be conducted by an independent Data Monitoring Committee (DMC) before proceeding with Stage 2 of the study.

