## Study Population

The study population will comprise approximately 1000 healthy US adults: up to 600 eligible subjects aged 50 to 59, a minimum of 200 subjects aged 60 to 64, as well as a minimum of 200 subjects aged 65 years and older.

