## 3. Objectives and Endpoints

### 3.1 Primary

The primary objectives are:

- To evaluate the safety and tolerability of a single injection of VAX-31 at 3 dose levels administered to healthy adults 50 years of age and older.
- To compare the safety of VAX-31 to that of PCV20 administered to 4 age groups:
  - Subjects 50 to 59 years of age
  - Subjects 50 years of age and older
  - Subjects 60 years of age and older
  - Subjects 65 years of age and older

Safety and tolerability will be assessed by measuring the incidence of solicited local and systemic AE, unsolicited AE, serious adverse events (SAE), new onset of chronic illness (NOCI), and medically attended adverse events (MAAE):

[REDACTED]

[REDACTED]

[REDACTED]

- Percentage of subjects reporting solicited local reactions within 7 days after vaccination (redness, swelling, and pain at injection site) in each age group
- Percentage of subjects reporting solicited systemic events within 7 days after vaccination (fever, headache, fatigue, muscle pain, and joint pain) in each age group
- Percentage of subjects reporting unsolicited AE within 1 month (30 days) after vaccination in each age group
- Percentage of subjects reporting SAE within 6 months after the vaccination
- Percentage of subjects reporting NOCI within 6 months after the vaccination
- Percentage of subjects reporting MAAE within 6 months after vaccination

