### **10.3 Treatment Groups**

Subjects will be randomized into 4 treatment groups:

- 250 subjects will receive VAX-31 Low Dose
- 250 subjects will receive VAX-31 Mid Dose
- 250 subjects will receive VAX-31 High Dose
- 250 subjects will receive PCV20

For Stage 1, there were no stratification factors. For Stage 2, randomization will be stratified by clinical site.

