2.3. Randomization Methodology

In Stage 1, a group of 64 subjects are planned to be randomized in a 1:1:1:1 allocation ratio i.e. 16 subjects in each VAX-31 dose level group and 16 in the PCV20 group. There will be no stratification factors.

In Stage 2, a total of 736 subjects, with a minimum of 200 subjects aged 60 to 64, along with a minimum of 200 subjects aged 65 years and older, are planned to be randomized in a 1:1:1:1 allocation ratio. The randomization will be stratified by site.

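### Stage 2 randomization is stratified by site but not by age group, so 65+ arm sizes are left to chance and the site-adjusted 65+ immunogenicity intervals are about 4–5% wider than they need be

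*Protocol*

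**What the plan says.** Protocol 6.8 leaves Stage 1 unstratified and then states: "For Stage 2, randomization will be stratified by each of the 25 clinical sites". Protocol 10.3 repeats it ("For Stage 2, randomization will be stratified by clinical site"), and SAP 2.3 agrees ("The randomization will be stratified by site"). SAP 6.2.3 lists no other stratification factor.

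Age nevertheless organizes the trial:

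- **Quotas.** The synopsis sets "up to 600 eligible subjects aged 50 to 59, a minimum of 200 subjects aged 60 to 64", and a minimum of 200 aged 65 and older.
- **Primary objective.** Protocol 3.1 includes "To compare the safety of VAX-31 to that of PCV20 administered to 4 age groups". The four groups are 50–59, 50+, 60+ and 65+.
- **Primary endpoints.** Solicited local reactions, solicited systemic events and unsolicited AEs are worded by age group. SAE, NOCI and MAAE are not.
- **Immunogenicity.** Protocol 10.7.1 and SAP 6.6 run the analyses for 50–59, 60+, 65+ and overall.

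The main immunogenicity model (Protocol 10.7.1, SAP 6.6.1) is an ANOVA with treatment and site as fixed effects. The ANCOVA adds log10 baseline titer. Neither contains age.

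On numbers, Protocol 6.8 says "See Section 10.3 for further details on the sample sizes within each age group". Section 10.3 gives only 250 per arm. Age-group totals do appear in Protocol 4.2 and 10.1, but no section gives them by arm.

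**The concern.** Age is known before randomization and has to be tracked to apply the quotas, but the 1:1:1:1 ratio is protected only within site. Site blocks ignore age, so the arm split among subjects aged 65 and older is close to a random draw from the Stage 2 list.

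This matters most for 65+, the smallest group with its own comparisons: at the minimum of 200 it has about 50 per arm and about 8 subjects per site. The planned model fits a fixed effect for each site. When the few older subjects at a site are split unevenly across arms, part of their information goes into estimating that site's effect and not the treatment contrast. Protocol section 10 compares the lower 95% limit of each geometric mean ratio (GMR) with 0.5 for shared serotypes and 2.0 for the added ones, so interval width has a direct use.

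In the 50+ and 60+ sets the issue is different: a chance difference in age mix between arms would go uncorrected, because the models have no age term.

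**Working it through.** **The plan's own probability figure.** The only probabilities given are for Stage 1 with 16 per arm: 1 − 0.85^16 = 0.926 and 1 − 0.90^16 = 0.815. These reproduce the stated 92% and 81%. Nothing comparable is given for any age group.

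**Inputs from the documents.** Stage 2 size is 736 + 200 = 936 (SAP 2.5 also gives 936), or 234 per arm. There are about 25 sites and at least 200 subjects aged 65+, all in Stage 2 because Stage 1 is limited to ages 50–64.

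**Inputs assumed.** Permuted blocks of 4 (8 also tried), equal or uneven site sizes, and age unrelated to site.

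**Step 1: 65+ arm sizes.** If site blocks carry no information on age, the count in one arm is hypergeometric, 200 drawn from 936 with 234 in the arm:

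- Mean = 200/4 = 50.
- Variance = 200 × 0.25 × 0.75 × (736/935) = 29.5, so SD = 5.4.

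Simulating the site-stratified blocks gives the same SD and the ranges below.

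| Strata | 95% range of a 65+ arm | Some arm below 40 |
|---|---|---|
| Site only | about 39–61 | about 10% of trials |
| Site × age | about 46–54 (blocks of 4), 45–55 (blocks of 8) | none seen |

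**Step 2: unadjusted comparison (the safety percentages).** Variance is proportional to 1/n1 + 1/n2, which is 2/50 = 0.0400 at 50 v 50.

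- 45 v 55: 0.0404, so width × √1.010 = 1.005.
- 40 v 60: 0.0417, so width × √1.042 = 1.021.
- Average over simulated trials with site-only strata: 1.005 (95th percentile 1.06). With site × age strata and blocks of 4: 1.001.

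The average unadjusted loss is about 0.5% of width for 65+. It is about 0.2% for 60+ and 0.1% for 50–59.

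**Step 3: planned treatment + site model, 65+.** Variance of one dose-versus-PCV20 contrast, in units of the residual variance σ², blocks of 4:

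| Sites | Site only | Site × age | Variance ratio | Width ratio |
|---|---|---|---|---|
| Equal | 0.04515 | 0.04068 | 1.110 | √1.110 = 1.054 |
| Uneven | 0.04493 | 0.04113 | 1.092 | √1.092 = 1.045 |

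In subjects, this is worth 200 × (1 − 0.04068/0.04515) = 20 with equal sites and 200 × (1 − 0.04113/0.04493) = 17 with uneven sites.

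A separate simulation, scaled to the 50 v 50 ideal of 0.04σ², gave variance ratios of 1.121/1.017 = 1.10 (equal sites) and 1.125/1.030 = 1.09 (uneven) with blocks of 4. With blocks of 8 the gain is smaller: 1.127/1.030 = 1.09 and 1.126/1.049 = 1.07. For 60+ the excess variance is 3–4%, or roughly 2% of width.

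**Step 4: scale.** With an assumed SD of 0.6 on log10 titer and a true GMR of 1, the unadjusted chance that the lower limit exceeds 0.5 is 71% at 50 v 50, 69% at 40 v 60 and 66% at 40 v 50. By comparison, having 50 rather than 250 per arm widens the interval by √(250/50) = 2.24 times.

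**The case against.** The case for leaving the design alone is a reasonable one.

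- **No bias.** Equal allocation gives equal expected arm sizes and unbiased comparisons in every age group. A reader might infer that the arms will be unbalanced, or the comparisons distorted, within each age group. The documents do not support that: only chance imbalance is possible. This stands.
- **Not every primary comparison is affected.** Three of six primary endpoints carry no age-group wording, and overall 50+ is itself a comparison group. The safety endpoints are summarized as percentages without a site-adjusted model, so the 9–11% does not apply to them. This stands.
- **The cost comes partly from the model.** The 65+ loss exceeds a fraction of a percent only because about 25 site effects are fitted in about 200 subjects. True, but that ANOVA is the protocol's main model, so its figure is the relevant one for the GMR intervals.
- **Nothing was promised.** Protocol 10.1 gives no statistical basis for the Stage 2 size, and SAP 6.2.4 says there are no formal hypothesis tests. This lowers the severity. It does not remove a cheap gain in a group the plan reports separately.
- **More strata have a price.** Three age levels at 25 sites make 75 strata with more part-filled blocks. In simulation, the average gap between the largest and smallest whole-trial arms rises from about 5.5 to about 8 subjects, against about 234 per arm. That is small.
- **It may be too late.** Protocol 6.8 describes Stage 1 in the past tense, so Stage 2 lists may already exist. The fix allows for this.

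**Conclusion.** The point holds, at low severity. Age group governs quotas and reporting, but it enters neither the Stage 2 strata nor the immunogenicity models. At the 65+ minimum of 200, arms would range over about 39–61. The planned site-adjusted 65+ contrasts would have about 9–11% more variance than under site-by-age strata, about 4–5% in interval width. Unadjusted safety comparisons lose about 0.5% of width on average, and the loss for 50–59 and 60+ is small.

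It would be wrong to conclude that the missing stratum is what limits 65+ precision; the number of subjects matters far more.

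The sizes rest on assumptions the documents do not settle: permuted blocks, a block size of 4 (blocks of 8 bring the variance gain down to about 7–9%), site sizes, age unrelated to site, and enrollment at the 65+ minimum. SAP 6.2.5, cited in SAP 3.2 for the age-group definition, was not in the text available for this review. The statement that age is not handled rests on Protocol 6.8, 10.3 and 10.7.1 and SAP 2.3, 6.2.3 and 6.6.1.

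**What to change.** 1. **Randomization (Protocol 6.8 and 10.3, SAP 2.3).** If the lists can still be changed, stratify Stage 2 by site and age group: at least 50–64 versus 65+, or 50–59, 60–64 and 65+. The cost is a re-specified list in the EDC system, which already needs age for the quotas, and the slightly looser whole-trial balance given above for three age levels. Two levels mean 50 strata instead of 75, so fewer part-filled blocks.
2. **Models (Protocol 10.7.1, SAP 6.2.3 and 6.6.1).** Whether or not the lists change, add age group as a fixed effect to the ANOVA and ANCOVA for the 50+ and 60+ sets. This costs one model term and corrects chance differences in age mix there. It does nothing for 65+ precision, which only the first change can recover.
3. **Cross-reference.** Print the planned numbers by age group in Protocol 10.3, or point 6.8 to Protocol 4.2 and 10.1, where the totals stand. This only supplies missing detail.

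If the sponsor keeps site-only strata, one sentence giving the reason would be enough.
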